Objectives	
Primary Objective:
 
To assess the response on one TPO-RA after switching from another.
 
Secondary Objectives:
 
To assess the patterns of response and switching.

	
To understand the preference of patients and doctors.
 
To study the safety profiles associated with rhTPO and eltrombopag after switching.
 
Exploratory Objectives:
 
To analyze the associations between clinical characteristics and response after switching.
 
To explore the effect of rescue medication on response after TPO-RA switching.

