- Rate of response at 3 months after switching, according to the reasons of switching
- Proportion of patients who achieved, regained, and maintained response at 3 months after switching
- Time to response from 1st TPO-RA switching for patients who switch due to lack of efficacy
- Duration of response from 1st TPO-RA switching for patients who switch due to lack of efficacy

Duration of response is defined as the time from when CR or R is achieved/regained to the time of relapse.

- Proportion of patients with any bleeding (WHO bleeding scale grade 1–4¹¹) and clinically significant bleeding (WHO bleeding scale grade 2–4¹¹)
- Total score of bleeding calculated according to the Bleeding Rating System⁷
- Patient and physician's treatment preference

At 6 weeks after switching, patients will be asked whether they prefer to continue treatment with rhTPO or eltrombopag, or whether they had no preference¹². In addition, patients who prefer one TPO-RA over the other will be queried on the reasons of preference (Patient preference questionnaire attached as Appendix 1).

At 6 weeks after switching, physicians will also be asked whether they prefer to further treat the patient with rhTPO or eltrombopag, or whether they had no preference, taking into account the patient's preference, response, and tolerability¹².

At 3 months after switching, the measurement will be applied again.

- Safety of treatment

The safety of treatment will be determined from adverse events summarized by incidence and severity, and from clinical laboratory evaluations, physical examinations and ophthalmological examinations carried out during scheduled study visits.

Exploratory endpoints:

- Association between clinical characteristics and response after switching

The following clinical characteristics will be compared between responders and non-responders at 6 weeks and 3-month after switching, respectively: gender (male vs female), age at 1st TPO-RA, time from diagnosis to 1st TPO-RA, lines of previous therapy before 1st TPO-RA, maximum 1st TPO-RA dose received vs. not received, splenectomy status (yes vs no), switch sequence (rhTPO to eltrombopag or vice versa), switching behavior, switch due to efficacy vs non-efficacy issues, and 1st TPO-RA failure vs loss of response.

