	
3 months after switching.
 
The observation period is 3-month for each patient enrolled. Response to 2nd TPO-RA will be assessed throughout the observation period with response at 6 weeks being the primary evaluation. Adverse events, including bleeding events, will be assessed and recorded together with concomitant ITP treatment. Preference of patients and doctors on the two TPO-RAs will also be assessed.

Investigational Drug Administration	
Patients will initiate eltrombopag treatment with a dose of 50 mg once daily. Dose adjustment of study medication will be allowed to maintain platelet counts between 50*10⁹/L and 250*10⁹/L.
 
Patients will initiate rh-TPO with a dose of 300 U/kg/d for \leq14d. Patients who attained stable PLT counts (\geq50*10⁹/L) in two consecutive tests will enter maintenance therapy, starting with every other day administration of rhTPO, then adjust dose interval to maintain platelet counts at 30-100*10⁹/L.

Dose Adjustment Guidelines	
The following information serves as a reference; actual dose adjustment will be conducted according to clinical practice in considering the medical condition of a patient:
 
Eltrombopag: refer to Table 2.
 
RhTPO:
 
At initial treatment, rhTPO will be suspended when platelet counts \geq100*10⁹/L. During maintenance therapy, patients with platelet counts $>$150*10⁹/L will suspend treatment until platelet counts drop to \leq150*10⁹/L. Dosing interval will be prolonged when platelet count is \geq100*10⁹/L to \leq150*10⁹/L. Dose modification is not required when platelet count is \geq30*10⁹/L to $<$100*10⁹/L¹³.

Patient Population	Chinese adult patients with primary immune thrombocytopenia who failed first-line corticosteroid therapy and received rhTPO and then switch to eltrombopag or vice versa.
Key Inclusion Criteria	
 • Age 18 years or older • Chinese ethnicity • Primary ITP diagnosed according to the current definitions ^{7, 8, 14, 15} • Failed initial glucocorticosteroid treatment, • Applying rhTPO or Eltrombopag as subsequent treatment • Switch from rh-TPO to eltrombopag or vice versa • Treatment on rhTPO for 14 days minimum or Eltrombopag for 4 weeks minimum, if the reason of switching is lack of efficacy or platelet count fluctuations • Available follow-up at least 6 weeks after switching

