Key Exclusion Criteria	
 • HIV positive status, or active infection of HBV or HCV • Suffering from a serious or progressive disease, which, in the investigator's judgment, put the subject at undue risk for participation in this study (i.e. cancer or pre-cancer, immunocompromised, uncontrolled diabetes, epilepsy, severe cardio-cerebrovascular disease(s) (i.e. stroke, idiopathic aortic stenosis, aneurysm, hypertrophic obstructive cardiomyopathy, ischaemic heart disease, tachyarrhythmias, severe heart failure [classified as NYHA III-IV], severe lung dysfunctions, etc)) • History of thrombosis plus two or more risk factors as defined in Caprini thrombosis risk assessment model ¹⁶ • Lactating or pregnant women, or WOCBP who are unwilling to use highly effective contraceptive measures during the study period • Abnormal liver and renal functions: AST or ALT or total bilirubin $\geq 1.5 \times$ ULN, and/or creatinine $\geq 176.8 \mu\text{mol/L}$ • Women of childbearing potential (WOCBP) that are pregnant or wish to become pregnant during the prospective phase of the study. • Other conditions which the investigator considers inappropriate for enrollment
Safety Monitoring and Reporting	
Adverse events (AEs) will be collected throughout the study period and classified according to the National Cancer Institute Common Terminology Criteria for Adverse Events, version 5.0
 
(https://ctep.cancer.gov/protocoldevelopment/electronic_applications/docs/CTCAE_v5_Quick_Reference_5x7.pdf)
 
Also, whether an AE fulfills the criteria of a SAE will be judged according to the definition of ICH-E2. All SAEs occur during the study period will be reported to the Sponsor's Pharmacovigilance contact within 24 hours upon knowledge of the investigator. The following information is the minimum requirement of reporting:
 
 • Patient identifier • Product name • SAE description including assessment of causal relationship and severity • Investigator name and contact details 
Women who become pregnant during the study have to immediately inform their physician and discontinue, as neither rhTPO nor Eltrombopag currently have sufficient data to inform a drug-associated risk of adverse developmental outcomes.

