Statistical Analysis	
Statistical analysis methods:
 
Statistical analysis will be conducted by SAS Version 9.2 or above. Descriptive statistics for continuous variables include minimum, maximum, mean ± standard deviation and median with inter-quartile ranges (IQR). Categorical variables will be described as frequencies and percentages. Percentage will be calculated based on non-missing data unless otherwise specified. Comparison between categorical variables will be performed using chi-square test or Fisher's exact test, while comparison between continuous variables will be performed using two-sample t test for parametric data and Wilcoxon rank sum test for non-parametric data. Logistic regression will be used to assess the association between clinical characteristics and outcome of response. Time-to-event data will be described by Kaplan-Meier survival curve with log-rank test for between-group comparison.
 
Unless specified, statistical testing will be carried out bilaterally with significance level alpha=0.05, i.e. a p-value of less than or equal to 0.05 will be considered as statistically significant. Methods of descriptive analysis and hypothesis testing will be selected according to the data characteristics. Transformations will be undertaken as needed.
 
Analysis sets:
 
Full Analysis Set (FAS): includes all patients who receive at least one dose of the 2nd TPO-RA and have response assessed at 6 weeks after switching
 
Safety Set (SS): includes all patients who receive at least one dose of the 2nd TPO-RA after switching.
 
Efficacy analysis will be conducted on FAS and safety analysis on SS.

Table 1 Time and Events

Study procedures	Screening	During Treatment				Safety follow-up after treatment suspension/stop	End-of-study Visit
Visit schedule	-14~1d	Every week \pm 3d	Every 2 weeks	Every 4 weeks	Every 8 weeks	Every week \pm 3d	12 weeks \pm 7d

			±3d	±4d	±4d		
Written informed consent	X						
Demographics	X						
Medical history	X						
Physical examination	X	X				X	X
Ophthalmologic examination	X						X
CBC (incl. platelet count)	X	X ^{a, b}		X ^b		X ^e	X
Peripheral blood smear	X						
Liver function tests (ALT, AST, TB)	X		X ^c	X ^c		X ^d	X
Other clinical chemistry (incl. Cr)	X						X
Coagulation tests	X				X		X
Thyroid function test	X						
HBV, HCV, HIV testing	X						
ECG	X						
Ultrasound (spleen)	X				X		X
Chest X-ray	X						
Bleeding assessment	X	X				X	X

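### Adverse events are summarised only as crude 3-month incidence, pooling time on and off the 2nd TPO-RA, so the two safety profiles may rest on unequal exposure

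*Combined protocol and SAP*

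**What the plan says.** - **Objective** (Objectives, secondary): "To study the safety profiles associated with rhTPO and eltrombopag after switching".
- **Measure** (Endpoints, Safety of treatment): "The safety of treatment will be determined from adverse events summarized by incidence and severity", with laboratory, physical and ophthalmological examinations. Under Statistical Analysis, "Categorical variables will be described as frequencies and percentages".
- **Population** (Statistical Analysis, Analysis sets): the Safety Set "includes all patients who receive at least one dose of the 2nd TPO-RA after switching". No minimum exposure is set.
- **Window**: "Adverse events (AEs) will be collected throughout the study period" (Safety Monitoring and Reporting), and "The observation period is 3-month for each patient enrolled" (Trial Design). Table 1 has a column headed "Safety follow-up after treatment suspension/stop", and its AE/SAE row is marked there.
- **Schedules** (Investigational Drug Administration): "Patients will initiate rh-TPO with a dose of 300 U/kg/d for" at most 14 days. Maintenance follows only for patients with counts of at least 50 (×10⁹/L throughout) on two consecutive tests, starting every other day. Eltrombopag is once daily with no day limit.
- **Status of these rules**: the dose-adjustment guidance is a reference only, and Trial Design has both drugs used according to label and clinical practice.

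The plan defines no treatment-emergent period, no split of events by on-drug or off-drug onset, no summary of exposure duration and no rate per unit of time.

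**The concern.** The safety objective concerns each drug, but the percentage planned is of patients with an event at any time in the 3 months after the switch. That percentage depends on three things: the event risk on drug, how long patients stay on drug, and what happens after they stop.

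A patient who receives 14 days of rhTPO and is then observed to day 84 contributes about 70 off-drug days to the rhTPO column. Trial Design counts bleeding as an adverse event, and footnote f of Table 1 shows that other ITP treatment may be in use. A bleed in week 8, or a reaction to another ITP treatment, would be reported under a drug stopped weeks before. Conversely, a drug taken briefly has less time to show its own toxicity.

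The Study Rationale suggests that the two side-effect profiles could differ, so readers will set the columns side by side. They would have no means of separating these influences.

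**Working it through.** The plan states no adverse-event rate, exposure time or safety precision target, so there is no figure of its own to reproduce.

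**1. On-drug time from the written schedule.** Observation is 12 weeks = 84 days. Counting every-other-day maintenance as on treatment:
- eltrombopag without a pause: 84 days;
- rhTPO reaching and staying in maintenance: 84 days;
- rhTPO not reaching maintenance: at most 14 days (14/84 = 17%).

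The documents give no rate of entry to maintenance. As an assumption, borrow the response estimate in Sample Size Justification, 70% (50% to 90%). Mean rhTPO treatment period = 0.70 × 84 + 0.30 × 14 = 63 days (49 to 77), or 75% (58% to 92%) of 84.

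**2. Effect on crude incidence.** Assume the same on-drug hazard h per week for both drugs, no off-drug events, eltrombopag for 12 weeks, and a fraction f of rhTPO patients on drug for 2 weeks only. Incidence over t weeks = 1 − exp(−h·t); the rhTPO figure is (1 − f) × 12-week value + f × 2-week value.

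| h per week | 12 weeks | 2 weeks | rhTPO, f = 20% / 30% / 50% | Gap in points |
|---|---|---|---|---|
| 5% | 45.1% | 9.5% | 38.0 / 34.4 / 27.3% | 7.1 / 10.7 / 17.8 |
| 2% | 21.3% | 3.9% | 17.9 / 16.1 / 12.6% | 3.5 / 5.2 / 8.7 |

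**3. Sensitivity, at h = 5% and f = 30% (gap 10.7 points).**
- Off-drug hazard half the on-drug hazard: the short-course patients have 1 − exp(−(0.10 + 10 × 0.025)) = 29.5%; rhTPO = 0.7 × 45.1 + 0.3 × 29.5 = 40.4%; gap 4.7.
- Instead, 30% of eltrombopag patients stop at week 6: 0.7 × 45.1 + 0.3 × (1 − exp(−0.30) = 25.9%) = 39.4%; gap 39.4 − 34.4 = 4.9 (unrounded inputs).
- Both together: gap 2.0 (1.3 to 3.4 for f = 20% to 50%).
- Off-drug hazard equal to on-drug: gap 0. Off-drug hazard double: 1 − exp(−(0.10 + 10 × 0.10)) = 66.7%; rhTPO = 0.7 × 45.1 + 0.3 × 66.7 = 51.6%; the gap reverses to −6.5.

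**4. Do the pausing rules give a direction?** In maintenance, rhTPO pauses above 150 until the count is back to 150 or less. Eltrombopag pauses only above 250 but restarts at 100 or less (Dose Adjustment Guidelines; Table 2). With an assumed 5-day halving time, pause = 5 × log2(peak / restart level):
- peak 200: rhTPO 2.1 days, eltrombopag none;
- peak 300: rhTPO 5.0 days, eltrombopag 7.9 days.

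The direction depends on the peak. Table 2 also allows eltrombopag every other day or with days off.

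**5. Does a per-week rate solve it alone?** Suppose 20% of patients on either drug have a first event, all at week 1. Person-weeks to first event or end of treatment, per patient:
- eltrombopag: 0.2 × 1 + 0.8 × 12 = 9.8;
- rhTPO at f = 20% / 30% / 50%: 0.2 + 0.8 × (10 / 9 / 7) = 8.2 / 7.4 / 5.8.

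The rate ratio, rhTPO to eltrombopag, is 1.20 / 1.32 / 1.69 although the risks are identical. A rate that assumes constant hazard can therefore create the opposite artefact.

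**The case against.** The best defence is that the study is descriptive. No between-drug adverse-event test is named, and Sample Size Justification disclaims comparing efficacy between the switch groups. Both drugs are used as in practice, and a short or intermittent rhTPO course is part of that regimen. Three-month incidence is then a valid description of risk after a switch. This stands, and is why the crude figure should be kept. It does not answer the objective of a safety profile for each drug.

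The gaps in the first table are also near the unfavourable end, because they keep every eltrombopag patient on drug and allow no off-drug events. With about 50 patients per sequence, the 95% half-width for a difference, 1.96 × √[p₁(1 − p₁)/50 + p₂(1 − p₂)/50], is about 15 to 19 points across those scenarios, and each gap lies inside its own. This stands too: the distortion may be hard to tell from noise.

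Some handling exists. SAE reports need a causality assessment, and Table 1 separates visits during treatment from those after suspension or stop. Neither is carried into a planned summary.

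A reader might go further and infer that the pausing rules themselves give rhTPO less on-drug time, so that crude incidence must make it look safer. The documents do not support that: the restart thresholds work the other way after a high peak, and actual exposure follows label and clinical practice. A reader might also conclude that safety statements should rest on the per-week rate. That can reverse the artefact, and an on-drug rate leaves out events after withdrawal, a risk the Endpoints section itself mentions under platelet count fluctuations.

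**Conclusion.** The gap in the plan is real and modest. It has a single crude incidence over a window that mixes on-drug and off-drug time, and its written schedule makes unequal exposure plausible through the 14-day limit for rhTPO patients who do not reach maintenance. Patients in stable rhTPO maintenance may have the same treatment period as eltrombopag patients.

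The 3 to 18 points rest on assumed hazards and an assumed share of short courses; the documents support neither that size nor a fixed direction. What is at risk is the side-by-side reading of the two profiles, not a planned test. The remedy is cheap enough that it should be adopted before analysis.

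**What to change.** In Endpoints (Safety of treatment) and Statistical Analysis, keep crude 3-month incidence and severity as the description of risk after a switch. Add, by switch sequence:

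- **(a)** duration of exposure to the 2nd TPO-RA;
- **(b)** adverse events by onset while on the 2nd TPO-RA or after its suspension or stop. For this table, scheduled every-other-day or longer intervals count as on treatment, and a window after the last dose is stated in advance;
- **(c)** as a supplementary measure, patients with a first on-treatment event per patient-week of exposure, with a 95% CI.

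State that any side-by-side reading uses these together, and not the crude incidence or the per-week rate alone.

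The cost is one extra table and the dates on which the drug was started, suspended, stopped and resumed. Table 1 does not list a dosing record, so the sponsor should confirm that these dates are captured; some record of on-drug status is already needed to apply its visit columns. The downside of (c) is its assumption of a roughly constant hazard. No visit or procedure is added, and no change to dosing or clinical rules is proposed.

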
Study Rationale	
According to the findings of mechanism-based studies, rhTPO competes with endogenous TPO for binding to TPO-R while eltrombopag has an additive effect with endogenous TPO¹⁰, indicating that the treatment mechanism and side-effect profiles could be somewhat different between these drugs^{9, 10}. Therefore, when there's a lack of response or when adverse events become a problem with one TPO-RA, switching to another TPO-RA provides useful information for the management of adult ITP patients^{8, 9}.
 
Khellaf et al. retrospectively reviewed data of 46 ITP patients who sequentially switched from eltrombopag to romiplostim (a TPO-RA similar to rhTPO in mechanism) or vise versa due to varying reasons including lack of efficacy (n=23), platelet-count fluctuations (n=11), side effects (n=4), and patient's preference (n=8). Switching was shown effective in 50-80% of the patients, with eradication of platelet fluctuations in 54% and side effects resolved in 100%¹. Another retrospective analysis of 26 ITP patients showed that for patients who switched the TPO-RA as a result of inefficiency (n=10), switching from romiplostim to eltrombopag led to 100% response rates, whereas switching from eltrombopag to romiplostim led to 66% response rates. The response rate was 100% in patients who switched due to side effects (n=5) or patient preference (n=8)¹⁰. In a study of 51 primary ITP adult patients switching from romiplostim to eltrombopag, response rate was 80% (41/51) with efficacy maintained for a median of 5.5 (range, 2-9) months in all patients who switched because of patient preference (n = 16), platelet-count fluctuation (n = 6) and side-effects (n = 4)⁹. Cantoni et al. analyzed clinical characteristics associated with response to the switch of TPO-RAs and found that lines of previous therapy, as well as disease duration would lower the probability to respond. According to the study, response was achieved/regained in 57.8% of patients who switched for efficacy issues and 80% who switched for non-efficacy issues; once response to the 2nd TPO-RA is achieved, it is possible to maintain long-term effect in these patients³.
 
Based on the clinical evidence, it is shown that switching from one TPO-RA to another, as well as sequential therapy, provides favorable outcomes of response and tolerability (evidence levels IIb, III)⁸. However, current studies almost exclusively focus on the effect of switching between romiplostim and eltrombopag; whether there is also absence of cross-resistance between rhTPO and eltrombopag remains to be investigated. In addition, clinical evidence on TPO-RA switching is proposed on the basis of retrospective studies. Therefore, we propose here an observational study with retrospective and prospective design to evaluate the response and safety profiles of switching between eltrombopag and rh-TPO in Chinese adult ITP patients; the preference of patients and doctors will also be assessed in this study.

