Endpoints	
Primary endpoint:
 
 ➤ Rate of response at 6 weeks after switching from rhTPO to eltrombopag or vice versa 
Response is defined according to the Chinese guidelines for treatment of adult primary immune thrombocytopenia as ⁷:
 
Complete response (CR): platelet count $\geq 100 \times 10^9/L$ and absence of bleeding.
 
Response (R): platelet count range $30-100 \times 10^9/L$, at least doubling of the baseline count, and absence of bleeding.
 
No response (NR): platelet count $< 30 \times 10^9/L$, or less than doubling of the baseline count, or bleeding.
 
The rate of response at 6 weeks includes the total proportion of patients who achieved CR and R at 6 weeks in the groups switch from rhTPO to eltrombopag and eltrombopag to rhTPO, respectively.
 
Secondary endpoints:
 
 ➤ Rate of response at 6 weeks after switching, according to the reasons of switching 
The reasons of switching include ³:
 
Lack of efficacy:
 
 -1st TPO-RA failure: no response to either one TPO-RA administered before switch -Loss of response: relapsed after transient response to 1st TPO-RA (relapse is defined as platelet count $< 30 \times 10^9/L$, or less than doubling of the baseline count, or bleeding, after the achievement of CR or R. The blood platelet count should be confirmed on at least two separate occasions, which is at least 1 day apart when used to define relapse ⁷) 
Platelet count fluctuations: unstable platelet counts necessitating rescue therapy or transient TPO-RA dose modifications/withdrawal with associated risk of either rebound thrombocytopenia/bleeding or thrombocytosis
 
Patient's preference
 
Development of adverse events necessitating 1st TPO-RA discontinuation
 
 ➤ Proportion of patients who achieved, regained, and maintained response at 6 weeks after switching 
Response achieved refers to patients who failed the 1st TPO-RA achieve CR or R at 6 weeks after switching.
 
Response regained refers to patients who lost response to the 1st TPO-RA achieve

CR or R at 6 weeks after switching.

Response maintained refers to patients who achieved CR or R with the 1st TPO-RA and still respond to the 2nd TPO-RA at 6 weeks after switching.

- Rate of response at 3 months after switching from rhTPO to eltrombopag or vice versa

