Sample Size Justification	
Total Planned Number of Patients: 100 patients (~50 patients in each switch sequence but not a strict 1:1 ratio)
 
➤ The purpose of this study is not to compare the efficacy differences between the two switch groups but to describe the rate of response, so the sample size cannot be calculated.

	
Sample size rationale:
 
 ➤ According to a published similar literature, it is estimated that about 100 patients can reveal a certain proportion of efficacy ³; ➤ Using the cross-sectional sampling method, the estimated response rate of these two drugs is ~70% (95% CI, 50%-90%), the sample size would be 80. So, 100 patients' size was decided taking the 20% drop-out rate into consideration. ➤ According to our previous study, it is expected to complete the observation of 100 patients within one and a half year.

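### The exploratory comparison of switch sequence between responders and non-responders is an unadjusted test of response between non-randomised groups; the plan does not tie it to reason for switching.

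*Combined protocol and SAP*

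**What the plan says.** - **Purpose.** Sample Size Justification states: "The purpose of this study is not to compare the efficacy differences between the two switch groups"; the aim given instead is to describe response. It plans "100 patients (~50 patients in each switch sequence but not a strict 1:1 ratio").
- **Primary endpoint.** The 6-week rate of CR plus R is reported "in the groups switch from rhTPO to eltrombopag and eltrombopag to rhTPO, respectively". No test is attached to it.
- **Exploratory endpoint.** Ten clinical characteristics are to be compared between responders and non-responders, at 6 weeks and again at 3 months. One is "switch sequence (rhTPO to eltrombopag or vice versa"). Efficacy versus non-efficacy reason for switching is another item in the same list.
- **Methods.** Statistical Analysis assigns chi-square or Fisher's exact tests to categorical comparisons, at two-sided 0.05. It names logistic regression for the association between characteristics and response, without saying which covariates enter together. For time endpoints it says: "Time-to-event data will be described by Kaplan-Meier survival curve with log-rank test for between-group comparison". The groups are not named.
- **Allocation.** Trial Design describes an observational study in which switching follows physician preference and usual practice.
- **Reason and response.** Study Rationale reports from a cited survey that "response was achieved/regained in 57.8% of patients who switched for efficacy issues and 80% who switched for non-efficacy issues".

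**The concern.** Cross-classifying responder status by switch sequence gives a 2×2 table, and testing it is the same as testing whether the response rate differs between the two sequences. The exploratory endpoint therefore brings in the comparison that the sample size section disclaims.

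The sequences are formed by clinical choice. If more patients in one direction switched because the first drug failed, that sequence would show lower response even if the second drugs worked equally well within each reason. Such an imbalance is plausible here: Background describes one drug as injected and the other as oral, patient preference is a listed reason for switching, and Study Rationale expects side-effect profiles to differ. The entry rule for patients switching for lack of efficacy or platelet fluctuation also differs by first drug (14 days on rhTPO, 4 weeks on eltrombopag).

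The risk is that a significant crude p-value is read as one drug working better after the other.

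**Working it through.** **The plan's own figures.** The plan gives no calculation for a sequence comparison. Its evaluable number is 80, and 80 / (1 − 0.20) = 100 reproduces the enrolment target. Splitting 80 about equally gives 40 evaluable per sequence, used below. (The basis of the 80 itself, "the estimated response rate of these two drugs is ~70% (95% CI, 50%-90%), the sample size would be 80", is a separate matter and plays no part here.)

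**Inputs**
- From Study Rationale: response 0.578 (efficacy reason) and 0.80 (non-efficacy reason), a difference of 0.222.
- From Statistical Analysis: two-sided alpha 0.05.
- Assumed, because the documents do not give it: the share *s* of efficacy switchers in each sequence, shown as a range.
- Assumed in order to measure false positives: no true sequence effect within reason.

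**Step 1: apparent gap.** Expected crude rate in a sequence = 0.578*s* + 0.80(1 − *s*), so the gap between sequences = 0.222 × (difference in *s*). For shares of 70% and 30%:
- 0.70 × 0.578 + 0.30 × 0.80 = 0.645
- 0.30 × 0.578 + 0.70 × 0.80 = 0.733
- gap = 0.222 × 0.40 = 0.089

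**Step 2: false rejection by the crude test.** This is the probability that the Pearson chi-square reaches p ≤ 0.05, summed exactly over all pairs of binomial outcomes. The stratified column is a Mantel-Haenszel test by reason, from 40,000 simulated trials per row.

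| Efficacy switchers, two sequences | Crude rates | Gap (points) | Crude rejection, 40 each | Crude rejection, 50 each | Stratified rejection, 40 each |
|---|---|---|---|---|---|
| 50% / 50% | 68.9% / 68.9% | 0.0 | 4.8% | 4.9% | 5.0% |
| 60% / 40% | 66.7% / 71.1% | 4.4 | 6.9% | 7.6% | 4.9% |
| 70% / 30% | 64.5% / 73.3% | 8.9 | 13.3% | 15.8% | 4.9% |
| 80% / 20% | 62.2% / 75.6% | 13.3 | 24.5% | 30.0% | 5.0% |

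Hand check for 70% / 30% at 40 each. The pooled rate is 0.689, so the null standard error is √(2 × 0.689 × 0.311 / 40) = 0.1035. The standard error under the two rates is √((0.645 × 0.355 + 0.733 × 0.267) / 40) = 0.1030. Then (0.0888 − 1.96 × 0.1035) / 0.1030 = −1.11, a tail of 13.4%. The opposite tail adds about 0.2 points. This agrees with the exact 13.3%.

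**Step 3: can the data support adjustment?** At 70% response, 80 evaluable patients give about 0.30 × 80 = 24 non-responders. That is too few for all ten listed characteristics in one model, but workable for sequence plus reason. In addition, first-drug failure versus loss of response is defined only among efficacy switchers, so the list cannot enter a single all-patient model as it stands. It reads more naturally as one-at-a-time comparisons.

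**Step 4: price in precision.** For the risk difference at 40 each, compare 95% half-widths. Crude is 1.96 × the standard error from Step 2. Stratified combines the two reasons with weights n₁n₂/(n₁ + n₂). At 70% / 30% the strata are 28 vs 12 and 12 vs 28, with equal weights:
- variance = 0.25 × (1/28 + 1/12) × (0.578 × 0.422 + 0.80 × 0.20) = 0.0120
- half-width = 21.5 points, against 20.2 crude

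The same formula gives 20.1 against 20.3 at 60% / 40%, and 24.6 against 20.1 at 80% / 20%.

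**The case against.** The strongest reply has four parts.

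1. **The comparison is disclaimed and exploratory.** A reader might infer that the plan sets up a head-to-head efficacy test of the sequences. It does not: the primary rates are described per sequence with no test, and sequence is one of ten exploratory characteristics. This stands and limits the point to that endpoint. It does not remove the test, because the general methods text supplies one for every categorical comparison.
2. **Adjustment is not ruled out.** Logistic regression is named, and reason for switching is in the same list. Response by reason is also a secondary endpoint at both times. So it would be wrong to say that the plan excludes adjustment. But nothing puts sequence and reason in one model or calls for response by reason within sequence, and the crude test is the one written down.
3. **The log-rank test.** A reader might take the between-group log-rank test as a second crude sequence comparison. The documents do not support that: its groups are undefined, and time to response and duration of response are already confined to lack-of-efficacy switchers, so the 57.8% versus 80% mechanism cannot act there. No change to the log-rank test is asked for on this ground.
4. **The size is conditional.** No mix of reasons by sequence is given; equal mixes give no bias, and 60% / 40% gives rejection close to nominal. The two rates are descriptive, from a cited survey, and Study Rationale notes that existing studies almost exclusively concern romiplostim and eltrombopag. Another small survey cited there found 100% versus 66% response by direction among 10 inefficacy switchers, so a real direction effect is possible. All of this stands. The no-effect assumption is there to measure false positives; it is not a claim about the drugs.

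**Conclusion.** The point holds for the exploratory endpoint. The plan contains an unadjusted test of response between non-randomised sequences, at odds with its stated purpose, and does not specify that reason for switching is taken into account. If the cited rates apply and the shares of efficacy switchers differ by 20 to 60 percentage points, the crude comparison shows a spurious gap of 4.4 to 13.3 points and rejects falsely in 7% to 25% of studies at 40 per sequence, against about 5% when stratified by reason. These figures rest on assumed mixes and on rates that may not transfer to rhTPO.

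A reader might go further and infer that the main result is biased. It is not: the per-sequence response rates are descriptive estimates and do not change. This is a worthwhile, low-cost improvement and not a flaw in the primary analysis.

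**What to change.** In the exploratory endpoint and Statistical Analysis, take one of two routes.

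- **Keep a test.** Replace the crude sequence comparison with a Cochran-Mantel-Haenszel test stratified by efficacy versus non-efficacy reason, or a logistic model containing sequence and reason. Tabulate response by reason within each sequence. Label the result exploratory and state that residual confounding remains, for example by lines of previous therapy and disease duration, which Study Rationale says lower the chance of response.
- **Drop the test.** Report response by sequence descriptively, without a p-value, in line with the stated purpose.

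Reason for switching is already collected, so the cost is a sentence or two of SAP text and minor programming. The price of adjustment is usually a slightly wider interval, about 1 point on the half-width at a 70% / 30% mix. It is larger (about 4.5 points) at 80% / 20%, where the sequences overlap little within reason.
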